Statistical analysis	
Data processing and statistical analysis will be carried out by the service provider, Axonal-Biostatem.
 
The statistical analyses will be described in a Statistical Analysis Plan (SAP) validated by the Sponsor and the Scientific Committee, prior to the freeze-in.
 
Statistical analyses will be performed after baseline freezing of the data with SAS® software (SAS Institute, NC, Cary, USA), version 9.4 or later.
 
Demographic and efficacy/performance analyses will be performed in the ITT population. The primary endpoint will be analyzed in PP (Per Protocol) and then validated in the ITT (intention to treat) population. The safety analyses will be performed in the safety population.
 
For quantitative variables, the usual statistics (n, missing n, mean, standard deviation (SD), median, first and third quartiles (Q1 and Q3), minimum and maximum) will be presented. IC95% may be

	
presented if relevant (especially for the primary endpoint).
 
For categorical variables, the usual statistics (n, missing n, frequency and percentage) for each modality will be provided.
 
Descriptive statistics will be provided in aggregate and by pump group.
 
The type 1 error, α, is set at 5% when the tests used will be two-sided (superiority) and α will be set at 2.5% when the tests will be one-sided in the case of Noninferiority (IC95%).
 
Analysis of the main objective
 
The non-inferiority analysis will be produced via an Ancova or mixed model on the Per-Protocol population and then on an intention-to-treat basis.
 
If non-inferiority is demonstrated, a superiority analysis will be conducted.
 
Analysis of secondary objectives
 
The secondary criteria will be described and then be the subject of mixed or Ancova models.
 
A non-inferiority analysis on HbA1c data and superiority analyses on Time in range, number of glycemic events, patient satisfaction will be performed.

Regulatory framework	ID-RCB number, CPP opinion, CNIL MR001 and RGPD compliance, information to the ANSM, approval of investigator contracts by the CNOM, transparency obligations
Logistics	CRO Axonal-Biostatem (Nanterre, France)

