7.3 VISIT 1: INCLUSION VISIT WITH INFORMED CONSENT

No study-specific procedures should be performed until informed consent has been obtained from the patient.

Study procedures at Visit 1 include the following assessments:

- Provide verbal information about the study procedures and objectives as well as those presented in the package insert, and ensure that the patient has the opportunity to ask questions
- Obtaining the signature of the informed consent
- Collect the following data using the eCRF:
 - Socio-demographic data
 - Age of diabetes, type, age of insulin therapy
 - HbA1C at the time of insulin pump prescription
 - Current model of pump used by the patient
 - Patient satisfaction with the current pump
 - Type of insulin used
 - Last HbA1C value less than one month old
 - Available glucose measurements (average of glucose measurements, estimated HbA1c, time in range)
 - Number of major glycemic events in the past month (as defined by the ADA) and in the past 6 months
 - Randomization of the patient in the pump group "Omnipod" or "Medtrum"

7.4 VISIT 2 (4 WEEKS): FOLLOW-UP VISIT AFTER 4 WEEKS OF PUMP USE.

- Collect tolerance data and possible adverse events, and report them as required from the eCRF
- Verify the conditions of use of the devices by the patient

- Collect time-stamped records of glucose values (as well as HbA1c estimated from average glucose measurements) and glycemic events, hypoglycemia and hyperglycemia, and insulin doses administered, from software provided by manufacturers
- Collect technical incidents with the device (catheter occlusion, alarms, pump detachment, pain, allergy, etc.)
- Patient satisfaction with their insulin delivery system
- Confirm or schedule the date of the V3 visit after 3 months of use
- Record all relevant data in the eCRF.

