4.4.3 Calculated/derived criteria

			2 = "More than 10 years
Number of years and months of treatment per pump	PUMP_D = Number of years * 12 + number of months	Time since starting pump therapy (in months)	Digital
Weight (kg) and height (cm)	BMI_D = (weight/height ²)*10000	Body Mass Index (BMI)	Digital
IMC_D	IMC4CL_D = -0 if BMI_D<18.5 -1 if BMI_D = [18,5 ; 25[-2 if BMI_D = [25; 30[. -3 if BMI_D >= 30	BMI (in classes)	0 = "Less than 18.5 1 = " [18,5 ; 25[" 2 = " [25 ; 30[" 3 = "Greater than 30
Tolerance variables	AL_PBTOL_D = -1 if the patient reported during the follow-up an irritation/itching problem or a redness problem or another adverse event -0 otherwise	Patient with at least one tolerance problem	0 = "No 1 = "Yes
HbA1c value measured in the laboratory at D0 and 3M	EVOL_HBA1C_D = HbA1c at M3 - HbA1c at D0	Evolution of HbA1c between D0 and 3M	Digital
Estimated HbA1c (FSL) (%)	EVOL_eHbA1c = HbA1c estimate at V2 - HbA1c estimate at D0 (will also be calculated for V3 and V4)	Evolution of HbA1c estimation between D0 and V2,V3,V4	Digital
Average blood glucose at different follow-up times	EVOL_GLYC_V2 = Average blood glucose at V2 - Average blood glucose at D0 (will also be calculated for V3 and V4)	Evolution of the average blood glucose level between D0 and V2, V3, V4	Digital
Average daily basal dose at different follow-up times	EVOL_BASAL_V2 = Average daily basal dose at V2 - Average daily basal dose at D0 (will also be calculated for V3 and V4)	Evolution of the average daily basal dose between D0 and V2, V3, V4	Digital
Average daily bolus dose at different follow-up times	EVOL_BOLUS_V2 = Average daily bolus dose at V2 - Average daily bolus dose at D0 (will also be calculated for V3 and V4)	Evolution of the average daily bolus dose between D0 and V2, V3, V4	Digital

Number of Boluses/day at different follow-up times	EVOL_NB_BOLUS_V2 = Number of Boluses/day at V2 - Number of Boluses/day at D0 (will also be calculated for V3 and V4)	Evolution of the number of Bolus/day between D0 and V2, V3,V4	Digital
Time of wearing the FSL	PORT_70sup = -1 wear time greater than 70%. -0 otherwise	FSL wear time greater than 70%.	0 = "No 1 = "Yes

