7.3 PATIENT CHARACTERISTICS AT INCLUSION

Inclusion parameters will be described globally and according to their group allocated by randomization on the **ITT population and then on the ITTm population**. Only demographic data will be described for **patients discharged with COVID-19**. Demographics

- Age (years)
- Gender (female; male)
- Type of diabetes (type 1; type 2)
- Time since the discovery of diabetes
- Time since discovery of diabetes (<5 years; 5-10 years; >10 years)

- Type of diabetes treatment:
 - Time since starting pump therapy (months)

Associated oral treatment

- For patients with type 2 diabetes:
 - Associated oral treatment (yes; no)
 - The list of associated oral treatments will be given via a listing

Clinical examination

- Weight (kg)
- Size (cm)
- BMI calculated (kg/m²)
- BMI calculated in classes (Lean: <18.5 kg/m²; Normal: 18.5-<25 kg/m²; Overweight: 25-<30 kg/m²; Obese: >= 30 kg/m²)
- Heart rate (bpm)
- Systolic blood pressure (mmHg)
- Diastolic blood pressure (mmHg)

Biological data

• Last HbA1c measurement in the laboratory (%)

Sensor data

- Estimated HbA1c (FSL) (%)
- FSL Wear Time (%)
- FSL wear time > 70% (yes; no)
- Average blood glucose (FSL) (mg/dl)
- Blood glucose SD (FSL) (mg/dl)
- Coefficient of variation of glucose values (%)
- Number of hypoglycemia
- Time spent in hypoglycemia <70 mg/dl (%)
- of normoglycemic values > 70-180 mg/dl (%)
- Time spent above >180 mg/dl (%)

Pump data

- Name of insulin used (Novorapid; Humalog; Apidra; Other)
 - If other, details will be given in a listing
- Average total daily insulin dose:
 - Average Daily Basal Dose
 - Average daily bolus dose
 - Number of Boluses/day

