7.4.2 Secondary endpoint analyses

Analyses will be performed on the ITTm population.

Each variable will be described globally and by pump group.

The secondary endpoints are:

1. HbA1c

The evolution of HbA1c (measured in the laboratory) between D0 and 3M will be described, and a comparison between the groups will be made using a Student's t test or a Mann and Whitney test.

2. Glucose level measurement

The mean blood glucose level and its standard deviation (Blood Glucose Deviation SD) will be described over each period (between V1 and V2, then between V2 and v3, then between V3 and V4) and over the total duration of the study (mean, median, standard deviation, Q1-Q3, minimum and maximum). The coefficient of variation of glucose values will also be described.

The evolution of the average blood glucose level compared to baseline will be described at each visit.

FSL wear time (%) will be described.

The % of blood glucose values spent in target (time in range: [70; 180]), hypoglycemia (<70mg/dl), and hyperglycemia (>180 mg/dl) will be described over each time period in each pump group and in the total population.

For these criteria, comparisons between groups will be made using the Student or Mann-Whitney test.

3. Glycemic events

The number of hypoglycemic events will be described overall and in each period by severity level (according to ADA consensus definitions) overall and in each pump group.

Comparisons between groups will be made using Student or Mann-Whitney tests.

The % of time spent in hyperglycemia will be described overall and over each period and in each pump group. Comparisons between groups will be made using Student's t test or Mann and Whitney test.

4. Device tolerance

The analysis of this criterion is detailed in section 7.4 of this document.

5. Incidents with devices

The following criteria will be described for each period and by pump group (after reclassification):

- Pump occlusion (yes; no)
 - If yes, number of times
- Pump detachment (yes; no)
 - If yes, number of times
- Complete stop / breakage of the pump (yes; no)
 - If yes, number of times
- Other pump malfunction (yes; no)
 - All other possible malfunctions will be listed.

6. Patient satisfaction

The following criteria will be described for each period and by pump group:

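### Time in range, time below 70 and time above 180 mg/dL are compared without baseline adjustment although D0 values exist; adjusting is a free gain in precision, and the protocol's two statements on the method need reconciling

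*SAP*

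**What the plan says.** **The planned test.** In SAP 7.4.2, item 2, the percentages in range, below 70 mg/dL and above 180 mg/dL "will be described over each time period in each pump group and in the total population". The comparison follows directly: "For these criteria, comparisons between groups will be made using the Student or Mann-Whitney test". No covariate is named.

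**Mean glucose is treated a little differently.** The same item says: "The evolution of the average blood glucose level compared to baseline will be described at each visit". SAP 4.4.3 defines the matching variable, "EVOL_GLYC_V2 = Average blood glucose at V2 - Average blood glucose at D0", and repeats it for V3 and V4. Among sensor measures, SAP 4.4.3 derives a change only for mean glucose and estimated HbA1c. It derives none for the three percentages.

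**Baselines exist.** Protocol 7.3 (Visit 1) collects "Available glucose measurements (average of glucose measurements, estimated HbA1c, time in range". SAP 7.3 lists the sensor data described at inclusion, including the percentage "of normoglycemic values > 70-180 mg/dl" and the times below 70 and above 180 mg/dL.

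**The protocol gives two methods.** The summary, under the analysis of secondary objectives, says: "The secondary criteria will be described and then be the subject of mixed or Ancova models". It adds that "superiority analyses on Time in range, number of glycemic events, patient satisfaction will be performed". Protocol 11.2.4 instead gives t-test or Mann-Whitney for comparing quantitative secondary variables. SAP section 6 reports no modification of the protocol's analyses.

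**The primary model, for contrast.** SAP 7.4.1 fits an ANCOVA with pump and baseline estimated HbA1c, and supplies PROC MIXED code.

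**The concern.** Every patient already uses the Omnipod and the FreeStyle Libre at entry, so the D0 sensor value comes from the same device in an established user. Some correlation between D0 and follow-up is to be expected. An unadjusted comparison of follow-up levels leaves that between-patient variation in the error term, and any chance difference between the arms at D0 passes partly into the reported pump difference.

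At stake is the width of the interval for time in range, which protocol 10.1 presents as a direction in which treatment monitoring is moving and which the protocol summary names for a superiority analysis. There is also a documentation question: a reader of the protocol summary would expect a model, a reader of section 11.2.4 would expect a two-sample test, and nothing in the SAP says that a choice was made.

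**Working it through.** **1. The plan's own figures reproduce.** The documents give a sample size only for the primary endpoint. With n per arm = 2(1.96 + 0.842)² SD² / 0.4²:
- SD 0.55 gives 29.7, so 30 per arm and 60 in all; 60 / 0.80 = 75 randomised, as stated.
- SD 0.8 gives 62.8, so 63 per arm and 126 in all, as stated in SAP 5.1.

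No power or sample size is stated for time in range or any other secondary endpoint.

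**2. Inputs for the secondary comparison.**
- Patients: 100 included (SAP 5.1), less the 4 COVID-19 discharges excluded from ITTm (SAP 7.1.3), leaves at most 96. At 1:1 that is at most 48 per arm.
- Test level: two-sided 5% for superiority (protocol summary).
- Assumptions not in the documents: SD of time in range 15 points, true difference 5 points, and a correlation ρ of 0.3 to 0.8 between D0 and follow-up.

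**3. Formulas.** Relative to the unadjusted comparison of levels, the variance of the pump difference is 1 − ρ² for ANCOVA and 2(1 − ρ) for a change from baseline. Standard error = 15 × √(1 − ρ²) × √(2/48), with ρ set to 0 for the unadjusted test. The 95% CI half-width is the t quantile times the standard error, and power is from the noncentral t distribution.

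**4. Results.**

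| Analysis | Residual SD | Variance ratio | CI half-width (points) | Power for 5 points |
|---|---|---|---|---|
| Unadjusted level | 15.0 | 1.00 | 6.08 | 37% |
| ANCOVA, ρ = 0.3 | 14.3 | 0.91 | 5.80 | 40% |
| ANCOVA, ρ = 0.5 | 13.0 | 0.75 | 5.27 | 46% |
| ANCOVA, ρ = 0.6 | 12.0 | 0.64 | 4.86 | 52% |
| ANCOVA, ρ = 0.7 | 10.7 | 0.51 | 4.34 | 62% |
| ANCOVA, ρ = 0.8 | 9.0 | 0.36 | 3.65 | 77% |

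The variance ratio needs only ρ, not the assumed SD or effect. A simulation of 4,000 trials at 48 per arm gave ratios of 0.78, 0.53 and 0.37 at ρ = 0.5, 0.7 and 0.8, close to the theoretical 0.75, 0.51 and 0.36.

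**5. In patients.** To match ANCOVA on 96 patients, the unadjusted test would need 96 / (1 − ρ²): about 105 at ρ = 0.3, 128 at 0.5, 188 at 0.7 and 267 at 0.8.

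**6. Chance imbalance.** Assuming the same SD of 15 at D0, the difference between arms at D0 has an SD of 15 × √(2/48) = 3.06 points. At ρ = 0.7, an imbalance of that size moves the unadjusted pump difference by 0.7 × 3.06 = 2.1 points.

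**7. Change in mean glucose.** If mean glucose is also compared as a change, its variance ratio 2(1 − ρ) is 1.40 at ρ = 0.3, 1.00 at 0.5 and 0.60 at 0.7. The corresponding ANCOVA ratios are 0.91, 0.75 and 0.51. The change score does worse at each value, and below ρ = 0.5 it does worse than the raw level.

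**The case against.** **The unadjusted test is valid.** Under randomisation it controls type I error, and its interval already allows for chance imbalance at D0. The secondary objectives are worded as descriptive, baseline sensor values will be tabulated by arm, and the primary analysis is not affected. All of this stands, and it limits the point to efficiency.

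**The gain may be small.** The documents give neither the correlation nor the length of the D0 sensor window on which it depends. At ρ = 0.3 the interval narrows by only about 5%. This stands too, which is why the table includes that row.

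**Readings that go further than the documents allow:**
- A reader of the protocol summary alone might infer that the SAP breaks with the protocol. It departs from the summary but follows section 11.2.4; the inconsistency lies within the protocol.
- Because estimated HbA1c derives from mean glucose, a reader might infer that an adjusted result on one and an unadjusted result on the other could differ only through method. They also differ in analysis set (PP against ITTm) and in time window (last 10 weeks against visit periods and total duration).
- A reader might infer that all sensor endpoints are tested only as raw levels. That is firm for the three percentages. For mean glucose, the change from baseline appears before the sentence on testing, so it may be compared as a change as well.
- A reader might take time in range as the only glycaemic measure planned for superiority. The summary also names the number of glycaemic events.
- A reader might extend the SAP's statement that power is below 80% to these endpoints. That statement concerns non-inferiority on the primary endpoint.

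**Conclusion.** The point holds as a free improvement. Time in range, time below 70 and time above 180 mg/dL are compared as unadjusted levels although their D0 values are available, and mean glucose is also compared without adjustment, as a level and possibly as a change. Adjusting each for its own baseline cuts the variance of the pump difference by a fraction ρ²: 9% at ρ = 0.3, 25% at 0.5 and 64% at 0.8. The power and half-width figures for time in range additionally rest on an assumed SD of 15 points, an assumed difference of 5 points and an even split of at most 96 patients. Neither the validity of the tests nor the primary conclusion is in question. Separately, the two protocol statements on the secondary method conflict, and the SAP does not say which it adopts.

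**What to change.** In SAP 7.4.2, item 2, replace the two-sample comparison with the primary model form for each sensor endpoint: follow-up value = D0 value + pump. Report the adjusted difference with its 95% CI for V1–V2, for V2–V3 and for the total randomised period up to V3. V3–V4 should stay out of these comparisons, because only patients randomised to Omnipod continue, using the Medtrum pump. Keep Mann-Whitney as a check where the percentages are skewed, as time below 70 mg/dL may well be.

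Record in SAP section 6 that the protocol summary and section 11.2.4 give different methods and that the baseline-adjusted model is adopted, before the database freeze.

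The cost is a few lines of SAP text and reuse of the existing PROC MIXED code with the outcome and baseline variables changed. The D0 values are already collected, and the model spends one degree of freedom.

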5 METHODOLOGY FOR STATISTICAL ANALYSIS

5.1 NUMBER OF SUBJECTS NEEDED (NSN)

The objective of a non-inferiority study is to demonstrate that the mean difference between the 2 devices remains small and clinically insignificant.

The average blood glucose level achieved in real life with the Omnipod pump corresponds to an estimated average HbA1c of 7.8% based on the experience of the three centers in the study's scientific committee, which is consistent with the literature. We can assume that the average blood glucose level on the Medtrum pump is the same as on the Omnipod pump. Setting the Δ threshold for non-inferiority at +0.4%, in accordance with FDA guidance (Guidance for Industry Diabetes Mellitus (Developing Drugs and Therapeutic Biologics for Treatment and Prevention)), if the upper threshold of the IC95% difference between the 2 pumps (Medtrum-Omnipod) exceeds Δ (i.e., 0.4), non-inferiority will not be demonstrated. Otherwise, the superiority of the Medtrum pump over the Omnipod pump can be tested, with a Δ ' threshold set at -0.3%.

On the basis of these assumptions, based on the so-called "Less is better" design with $\alpha = 2.5\%$, $\beta = 20\%$, and a standard deviation (SD) set at 0.55, the calculation of the necessary number of (analyzable) subjects was 60 patients (30 in each group).

Assuming that 20% of patients could not be analyzed (major discrepancies, missing data, lost to follow-up), the number of patients to be randomized was 75.

100 patients were finally included; to confirm our standard deviation hypothesis, a descriptive analysis of baseline HbA1c data for the entire population was performed in a blinded fashion at the end of the inclusion period. The standard deviation of the HbA1c estimate (FSL) was equal to 0.8.

With regard to the other assumptions of the protocol:

- Risk of first kind: 2.5%.
- Statistical power: 80%.
- Non-inferiority limit Δ : +0.4
- Assumed value of the difference between the two pumps: 0

The sample of patients needed for the study is estimated at 63 patients per group, for a total of **126 analyzable patients**.

As the study cannot include more than 100 patients, the statistical power of the study will be less than 80%.

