5.2 GENERALITIES FOR STATISTICAL ANALYSIS

Depending on the nature of the criteria studied, the descriptive statistics will be as follows: For categorical data: number of individuals, number of missing values, frequency and percentages of each of the variable's terms (excluding missing data in the denominator). Twosided 95% confidence intervals will be provided when deemed appropriate. Percentage will be presented to one decimal place.

Statistical analysis of quantitative data: number of individuals, number of missing values, mean, standard deviation, median, quartiles, minimum and maximum. The data will be presented as follows: 1 decimal place more than the original variable for mean and standard deviation, 0 for median, quartiles, min and max.

Statistical analyses will be performed using SAS® software, version 9.4, SAS Institute, NC, Cary, USA.

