7.1.3 Populations of analysis

Analysis populations will be presented with the number of patients in each treatment group. Intent-to-treat (ITT) population: all included and randomized patients who used the pump device at least once.

Intent-to-treat (ITTm) population: ITT population with exclusion of the 4 patients discharged due to COVID-19.

Population Per Protocol (PP): ITT patients with no major protocol deviations.

Tolerance population: all patients who have used the pump device at least once.

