8 STATISTICAL TABLE TEMPLATES

The tables will be presented in the form :

Table xx: Description of quantitative variables	
---	--

		Group A N=xxx	Group B N=xxx	Total N=xxx	p-value
Variable 1	Ν	Х	Х	Х	
	Missing	Х	Х	Х	
	$Mean \pm SD$	$xx.xx \pm xx.xx$	$xx.xx \pm xx.xx$	$xx.xx \pm xx.xx$	
	Median	XX.XX	XX.XX	XX.XX	
	Q1; Q3	xx.xx ; xx.xx	xx.xx ; xx.xx	xx.xx ; xx.xx	
	Min; Max.	xx.xx ; xx.xx	xx.xx ; xx.xx	xx.xx ; xx.xx	

		Group A	Group B	Total	
		N=xxx	N=xxx	N=xxx	p-value
Variable 2	Ν	Х	Х	Х	
	Missing	Х	Х	Х	
	Mean \pm SD	$xx.xx \pm xx.xx$	$xx.xx \pm xx.xx$	$xx.xx \pm xx.xx$	
	Median	XX.XX	XX.XX	XX.XX	
	Q1; Q3	xx.xx ; xx.xx	xx.xx ; xx.xx	xx.xx ; xx.xx	
	Min; Max.	xx.xx ; xx.xx	xx.xx ; xx.xx	xx.xx ; xx.xx	

The 95% Confidence Intervals can be presented in the tables. *Table xx: Description of categorical variables*

		Group A	Group B	Total	
		N=xxx	N=xxx	N=xxx	p-value
Variable 3	Ν	Х	Х	Х	Х
	Missing	Х	Х	Х	Х
	Modality 1	xx (xx.x%)	xx (xx.x%)	xx (xx.x%)	xx (xx.x%)
	Modality 2	xx (xx.x%)	xx (xx.x%)	xx (xx.x%)	xx (xx.x%)
Variable 4	Ν	Х	Х	Х	Х
	Missing	Х	Х	Х	Х
	Modality 1	xx (xx.x%)	xx (xx.x%)	xx (xx.x%)	xx (xx.x%)
	Modality 2	xx (xx.x%)	xx (xx.x%)	xx (xx.x%)	xx (xx.x%)
	Modality 3	xx (xx.x%)	xx (xx.x%)	xx (xx.x%)	xx (xx.x%)

The 95% Confidence Intervals can be presented in the tables. *Table xx: Description of IS by SOC and PT*

	Total (N=xxx)		
SOC and PT			
	EI	n	%
	(1)	(2)	(3)
TOTAL	XX	XX	XX.X
SOC 1	XX	XX	XX.X
SOC 1 - PT 1	XX	XX	XX.X
SOC 1 - PT 2	XX	XX	XX.X
	XX	XX	XX.X
SOC 2	XX	XX	XX.X
SOC 2 - PT 1	XX	XX	XX.X
SOC 2 - PT 2	XX	XX	XX.X
	XX	XX	XX.X

(1) Number of EIs

(2) Number of patients with at least one AE

(3) % of patients with at least one AE

9 **BIBLIOGRAPHY**

1. CNEDiMTS opinion of May 30, 2017. External, portable, programmable insulin pumps.

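### No Medtrum minus Omnipod difference or confidence interval is required for any compared secondary endpoint, and the SAP drops the protocol's non-inferiority analysis of HbA1c without declaring it

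*SAP*

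**What the plan says.** SAP 7.4.2 sets the population first: "Analyses will be performed on the ITTm population". SAP 7.1.3 defines that set as the "ITT population with exclusion of the 4 patients discharged due to COVID-19".

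The comparisons in SAP 7.4.2 are:

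- Laboratory HbA1c, change from D0 to month 3: "a comparison between the groups will be made using a Student's t test or a Mann and Whitney test".
- Mean glucose, its variability, and time in, below and above range: "For these criteria, comparisons between groups will be made using the Student or Mann-Whitney test".
- Hypoglycaemic events, time in hyperglycaemia, insulin doses and (where relevant) satisfaction scores: the same pair of tests.

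None of these items names a difference, an interval or a margin. The section 8 templates for quantitative and categorical variables have columns for Group A, Group B, Total and p-value.

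Intervals appear only as options. Section 8 adds under the templates that "The 95% Confidence Intervals can be presented in the tables". SAP 5.2, in its paragraph on categorical data, says "Twosided 95% confidence intervals will be provided when deemed appropriate". Protocol 11.2.1 also leaves them to discretion, with the primary endpoint chiefly in mind.

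The protocol planned more. Its synopsis, under analysis of secondary objectives, foresees mixed or ANCOVA models, a non-inferiority analysis of HbA1c, and superiority analyses of time in range, glycaemic events and satisfaction. Protocol 11.2.4 says that any secondary non-inferiority analysis uses the primary method, which sets the 95% interval of a difference in LS means against the bound. SAP section 6, reserved for changes to the protocol's analyses, declares none.

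**The concern.** The trial asks whether the new pump is no worse than the one patients already use. A test of zero difference does not answer that. A large p-value can come from a difference near zero or from an imprecise estimate of a material loss, and the p-value does not tell them apart. The interval does.

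Laboratory HbA1c carries the most weight here. The primary endpoint is a sensor-derived estimate of HbA1c, so the laboratory value is its natural check, and it is on the scale of the trial's 0.4 margin. With only a p-value planned, that check cannot be set against the margin. It is also the endpoint for which the protocol had planned an interval-based analysis.

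**Working it through.** **Reproducing the plan's own figures.** Per-group size for non-inferiority of means with true difference 0 is n = 2 × [SD × (1.960 + 0.842) / Δ]², with Δ = 0.4.

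- SD 0.55: n = 29.7, rounded up to 30 per group. 60 / (1 - 0.20) = 75 randomised. Both match SAP 5.1.
- SD 0.8: n = 62.8, rounded up to 63 per group, 126 in all. This matches SAP 5.1.

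**Inputs for the illustration on laboratory HbA1c change.**

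- n = 48 per arm: 100 included (SAP 5.1) less 4 (SAP 7.1.3), divided by 2. This assumes an even split and no other loss.
- SD of change = 0.8. This is an assumption. SAP 5.1 gives 0.8 for the sensor estimate at baseline, and the documents give no SD for laboratory change. The planning value of 0.55 is the alternative.
- Margin 0.4 (SAP 5.1). Positive differences mean Medtrum is worse.

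**Precision.** SE = SD × √(2/n). The half-width is t(0.975; 2n - 2) × SE, with t = 1.986 at 94 degrees of freedom.

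- SD 0.8: SE = 0.8 × √(2/48) = 0.1633; half-width = 0.324.
- SD 0.55: SE = 0.55 × √(2/48) = 0.1123; half-width = 0.223.

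**An observed difference of +0.30.**

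- SD 0.8: t = 0.30/0.1633 = 1.84, p = 0.069. CI = 0.30 ± 0.324 = -0.02 to +0.62. Not significant, and the upper bound is past 0.4.
- SD 0.55: t = 0.30/0.1123 = 2.67, p = 0.009. CI = 0.30 ± 0.223 = +0.08 to +0.52. Significant.

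**What p > 0.05 leaves open at SD 0.8.** It means an observed difference between -0.324 and +0.324. The upper bound is below 0.4 only if the observed difference is below 0.4 - 0.324 = +0.076. Observed differences from +0.076 to +0.324 are non-significant and do not exclude 0.4. The largest upper bound compatible with p > 0.05 is 2 × 0.324 = 0.65.

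**Chance of p > 0.05 when the true difference is +0.4** (non-central t, non-centrality 0.4/SE).

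| SD of change | n per arm | Non-centrality | P(p > 0.05) |
|---|---|---|---|
| 0.8 | 48 | 2.45 | 32% |
| 0.8 | 40 (20% of 100 lost) | 2.24 | 40% |
| 0.55 | 48 | 3.56 | 6% |

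**Sensitivity to the borrowed SD.** If the SD is 0.8 at both visits, the SD of change is 0.8 × √(2(1 - r)), where r is the correlation between visits. An SD of change of 0.8 therefore corresponds to r = 0.5. At 48 per arm, +0.30 gives p = 0.069 at r = 0.5, 0.020 at r = 0.7 and 0.005 at r = 0.8. It becomes significant above r of about 0.57.

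**The case against.** Several points on the other side are sound.

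- A reader might infer that a non-significant result excludes nothing. It does exclude large losses: above about 0.65 under the SD 0.8 assumption. The templates also print N, mean and SD by group, so an unadjusted t interval can be rebuilt for change scores. A Hodges-Lehmann shift or a baseline-adjusted difference cannot be rebuilt from those summaries.
- A reader might infer that most secondary tests will be non-significant whatever the truth. The documents do not support that. The shortfall conceded in SAP 5.1 concerns the primary analysis, and no power is given for any secondary endpoint. In the illustration a true +0.4 is detected in about 68% of trials.
- A reader might infer that the sponsor will present p > 0.05 as proof of no harm. Neither document says so. The secondary objectives are descriptive, and the protocol synopsis treats time in range, events and satisfaction as superiority questions, for which a zero-difference test is an ordinary tool. Protocol 11.2.4 itself allows t or Mann-Whitney tests for comparing quantitative variables.
- Device incidents and tolerance have no between-pump test named in the SAP text, so the point does not extend to them.

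These points limit the reach and size of the concern. They do not supply an interval: the confidence-interval wording is permissive throughout, and none of it refers to a between-pump difference. Nor do they explain why the HbA1c non-inferiority analysis is absent from the SAP.

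**Conclusion.** The point holds in a limited form. SAP 7.4.2 and section 8 pre-specify no between-pump estimate or interval for laboratory HbA1c change, glucose measures and time in range, hypoglycaemic events, time in hyperglycaemia, satisfaction or insulin dose. For laboratory HbA1c this departs from the protocol without being declared. That reading takes the synopsis's HbA1c analysis to mean the laboratory value, the HbA1c measure in the protocol's list of secondary endpoints.

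The size depends on an SD that the documents do not give. At 48 per arm, a true loss equal to the margin goes undetected in about 32% of trials if the SD of change is 0.8, and in about 6% if it is 0.55. The need for an interval does not depend on that figure, because at any SD a p-value for zero difference does not show whether 0.4 is excluded. This is a correction that should be made; it does not affect the primary analysis.

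**What to change.** 1. In SAP 7.4.2 and the section 8 templates, add a column for the difference Medtrum minus Omnipod with its two-sided 95% CI, beside the p-value, for each compared secondary endpoint. Use a baseline-adjusted ANCOVA difference where a baseline exists, the Hodges-Lehmann shift with its CI where Mann-Whitney is used, and a risk difference with CI for any yes/no item that is compared. State the direction in words, since SAP 5.1 and 7.4.1 write the subtraction in opposite orders.
2. Restore the protocol's non-inferiority analysis of HbA1c for the laboratory value, naming its margin and population, or list its removal with a reason in SAP section 6.
3. State that p > 0.05 on a secondary endpoint is not evidence of non-inferiority and that interpretation rests on the interval.

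No new data are needed. The cost is one table column and a few sentences, and some intervals will look wide.
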